
Criteria for Evaluation: (Efficacy, safety, stopping rules, etc.)
	
SAFETY: To assess safety the NCI Common Terminology criteria version 4.0 June 2010 will be applied. Particular attention to serious adverse events and infections will be given. Patient evaluations will include: vital sign measurement, physical examination, and laboratory parameters for hematology and routine chemistries.
 
EFFICACY: To assess efficacy, the primary endpoint will be the Definition of Improvement (DOI): 3 of any of the 6 core set measures improved by $\geq 20\%$, with no more than 2 of the core set measures worsening by $\geq 25\%$ (worsening measure cannot include the muscle strength).
 
STOPPING RULES: Subjects in this study may be discontinued for any of the following reasons:
 
• Severe allergic reaction to the study medication• Participation in another investigational drug study• Any medical condition which, in the opinion of the investigator, warrants discontinuation from the study for the safety of the patient, either as a cause of the study drug or protocol violations, including non-compliance or inability to perform protocol-required procedures• Voluntary withdrawal (withdrawal of consent)• Pregnancy• If 3 or more patients develop a serious adverse event thought to be related to study drug, no new patients will be enrolled into the study until the adverse events have been reviewed by the Medical Safety Officer and/or Data Safety Monitoring Board.
---	--

Statistics:	n-randomized trial to assess the safety and efficacy of subcutaneous abatacept in 10 patients (children and adults) with juvenile-onset refractory dermatomyositis (JDM). Summary statistics will be generated to describe the study data. Descriptive statistics, including measures of central tendency (e.g. means, medians) and estimates of spread (e.g. standard deviations) will be used for continuous variables, including reporting of adverse event frequencies, core set measure assessments, and demographic and clinical variables. Non-parametric Wilcoxon signed rank tests will be used to investigate changes in continuous variables. 95% confidence intervals will be calculated for all point estimates.
--------------------	---

APPENDICES

- Appendix A Bohan and Peter Criteria for diagnosis of dermatomyositis
- Appendix B Proposed new classification criteria for IIM
- Appendix C IMACS and PRINTO Core Set Activity Measures

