2.1 PRIMARY OBJECTIVE

AIM: To assess the safety and efficacy of subcutaneous abatacept in an open-label trial of refractory JDM in 10 adults and children.

- **Hypothesis A: *Abatacept will be well-tolerated and safe in treatment–refractory JDM patients.*** For this, the NCI Common Terminology criteria version 4.0 June 2010 will be applied. Medical records will be reviewed for the 6 months prior to enrollment to obtain adverse events prior to beginning abatacept, which will be compared to any adverse events that develop after abatacept was initiated. Particular attention will be given to serious adverse events and infections. Patient evaluations will include: vital sign measurement, physical examination, and laboratory parameters for hematology and routine chemistries.
- **Hypothesis B: *Patients will clinically improve after treatment with abatacept.*** We hypothesize that at least 6 of 10 patients will meet the myositis preliminary definition of improvement after receiving 24 weeks of therapy with abatacept.

Definitions of improvement (DOIs) for clinical trials in IIM have recently been proposed by the IMACS Group (International Myositis Assessment and Clinical Studies) for adult and pediatric myositis utilizing six core set measures among five domains of myositis disease activity (38) (**see Appendix C**). They are:

- a) Physician global disease activity;
- b) Parent/patient global disease activity;
- c) Muscle strength, utilizing manual muscle strength testing (MMT8);
- d) Physical function assessment using the (Childhood) Health Assessment Questionnaire (CHAQ);
- e) Laboratory assessment using the most abnormal serum muscle enzyme level; and
- f) Extra-muscular disease activity using the Myositis Disease Activity Assessment Tool (MDAAT). (see section 14.0: assessment tools: description) (39)

For this clinical trial, the primary endpoint will be the published Definition of Improvement (DOI): 3 of any of the 6 core set measures improved by $\geq 20\%$, with no more than 2 of the core set measures worsening by $\geq 25\%$ (worsening measures cannot include the muscle strength). (Appendix D1) (38)

The PRINTO Group (Pediatric Rheumatology International Trials Organization) has developed and validated a core set of outcome variables for the evaluation of response to therapy in JDM. (40) (Appendix C)

The additional PRINTO core set activity measures are:

- 1) Childhood Myositis Assessment Scale is used as a measure of strength;

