- 2) A health related quality of life measure, CHQ-PF50, is used and
- 3) Disease Activity Score (DAS) is used as a measure of global activity (42)

PRINTO also has a definition of minimal clinical improvement (20%), moderate (50%) and major (70%) improvement (41) (Appendix D).

PRINTO has also defined clinically inactive disease (41) as creatine kinase ≤ 150 (within normal limits), CMAS ≥ 48 , MMT ≥ 78 and Physician Global Activity VAS ≤ 0.2 . (41) (Appendix D)

The frequency of minimal, moderate and major improvement by the DOIs, with 20%, 50% and 70% change, as well as clinically inactive disease by the PRINTO criteria will also be examined in this trial.

Finally, the DOIs are currently undergoing revision in an ACR-EULAR project that is combining the efforts of IMACS and PRINTO. New definitions of minimal, moderate and major improvement have been developed and are expected to be finalized within the coming year. These newly-developed definitions will be added to the criteria as a secondary efficacy outcome measures for this trial (**Appendix D2**). Other criteria found to perform very highly in the ACR-EULAR project will be used as secondary endpoints in this trial (Appendix D2).

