	c. Has the patient had intolerance or an inadequate response to methotrexate at least 15 mg/week or 0.3 mg/kg or 15 mg/m ² / week for at least 3 months?
	d. Has the patient had intolerance or an inadequate response to mycophenolate mofetil at least 30 mg/kg/d or 1000 mg bid for at least 3 months?
	e. Has the patient had intolerance or an inadequate response to cyclophosphamide at least 1.0 mg/kg/d poor 500 mg/m ² /month IV for at least 3 months?
	f. Has the patient had intolerance or an inadequate response to oral tacrolimus for at least 3 months?
	g. Has the patient had intolerance or an inadequate response to cyclosporine at least 2.5 mg/kg/d for at least 3 months?
	h. Has the patient had intolerance or an inadequate response to IVIG at least 1.0 g/kg/month for at least 3 months?

	i. Has the patient had intolerance or an inadequate response to an anti-TNF agent (including Etanercept, Infliximab, Humira, etc) for at least 3 months?
	j. Has the patient had intolerance or an inadequate response to 2 infusions of Rituximab (375mg/m ² (for 4 doses), or 500 mg/m ² or 1000 mg for 2 doses)?
6	Considering 6a-6f, Does the patient have a moderately active disease (MD global VAS with a minimum value of 2,5 cm on a 10 cm scale plus another 2 other abnormal Core set Measures as listed above (7b-7f)
	a. Does the MD global VAS have a minimum value of 2.5 cm on a 10 cm scale
	b. Is the MMT-8 score no greater than 125/150
	c. Does the Patient/parent Global VAS have a minimum value of 2.0 cm on a 10 cm scale
	d. Does the CHAQ/HAQ disability index have minimum value of 0.25
	e. Is at least one of the muscles enzymes (including CK, aldolase, LDH, AST and ALT) elevated at a minimum level of 1.3 times the upper limit of normal. If more than one muscle enzyme is identified as being elevated and meeting the above guidelines, then the most abnormal will be selected and this enzyme will be the target enzyme followed to evaluate disease improvement or worsening.
	f. Does the Global extra-muscular disease have a score with a minimum value of 2 cm on a 10 cm VAS scale.
7	Is the prednisone dose stable for 4 weeks prior to the screening visit? (recommended dose ≤ 1.0 mg/kg/day)

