- Collect pre -treatment research blood samples for Immunophenotyping (T, B cells and macrophages), gene expression, and cytokine/chemokine analysis (see Section 3.1.h)
- Myositis specific and associated autoantibody testing
- Collect pre -treatment blood samples for immunogenicity
- Pregnancy test for females of child bearing potential (where applicable)
- Administer first dose of study medication and observe after the injection for at least 15 minutes
- Schedule and instruct the subject to return for the next visit, teaching injection technique, review medication administration log.

Phone follow-up #1 (14 days (+/- 7 days after visit 1)

- Adverse events will be reviewed and recorded (NCI Common Toxicity criteria version 4.0).

Phone follow-up #2 (will occur 28 days (+/- 7 days) after visit 1.

- Adverse events will be reviewed and recorded.

Visit 2 (week 6) will occur 42 days (+/-10 days) after visit 1

- Review concomitant medication and query for adverse events and document in CRF
- NCI Common Toxicity Assessment
- Obtain vital signs (HR, BP, RR, oral temperature and weight) and if indicated, by history of shortness of breath or lung disease, pulse oximetry)
- Medical history and perform a full physical examination
- Collect urine sample for pregnancy test for females of child bearing potential prior to administration of study medication (where applicable)
- Core set activity measures: physician global activity, patient/parent global activity, manual muscle testing (MMT-8), CMAS, HAQ/CHAQ, MDAAT, muscle enzymes, CHQ PF-50/SF- 36, and Disease activity score (DAS), physician global damage (VAS)
- Dermatology assessment: CDASI, photographs of skin rashes
- Quality of life questionnaires: CHQ PF-50/SF- 36, DLQI, PROMIS/fatigue, and Peds QL fatigue
- Physician and patient/parent assessment of study outcome

- Obtain blood samples for Chem-20, GGT, CK, aldolase, LDH, CBC with diff., von Willebrand Factor antigen level [**may be performed at home institution, up to 10 days before the visit date**]
- Urinalysis
- Collect urine sample for pregnancy test for females of child bearing potential (where applicable)
- Prednisone taper may commence using a predetermined schedule (section 5) if the patient has achieved the Definition of Improvement (DOI) and is rated by the study physician as at least minimally improved.
- Review log of medication self-administration and pharmacy to dispense study medication needed before next visit

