14.0 ASSESSMENT TOOLS: description

The core assessment tools are available on the International Myositis Assessment and Clinical Studies (IMACS) Group website at:

1. IMACS website:
<http://www.niehs.nih.gov/research/resources/imacs/imacsforms/>
2. Disease activity core set measures:
<http://www.niehs.nih.gov/research/resources/imacs/diseaseactivity/index.cfm>
3. Disease damage core set measures:
<http://www.niehs.nih.gov/research/resources/imacs/diseasedamage/index.cfm>

Manual Muscle Testing. (MMT): MMT has been widely used in myositis therapeutic trials and clinical studies, previously as a primary end point (17) and more recently as part of a composite end point of core set measures (38). MMT has been modified to a shorter version called MMT-8, in which quantitative testing of eight proximal, distal and axial muscle groups tested unilaterally (using a 0-10 point scale) closely approximate a total MMT score of 26 groups tested bilaterally(42).

MMT- 8 is a set of 8 designated muscles tested unilaterally (potential score 0-80) or bilaterally (potential score 0-150)

Muscle Groups	Right (0 – 10)	Left (0 – 10)	Axial (0 – 10)
Axial Muscles (0 – 10)			
Neck Flexors	X	X	0-10
Proximal Muscles (0 – 100)			
Deltoid	0-10	0-10	X
Biceps brachii	0-10	0-10	X
Gluteus maximus	0-10	0-10	X
Gluteus medius	0-10	0-10	X
Quadriceps	0-10	0-10	X
Distal Muscles (0 – 40)			
Wrist Extensors	0-10	0-10	X
Ankle dorsiflexors	0-10	0-10	X
MMT-8 score (0 – 150)	0-70	0-70	0-10

Myositis Disease Activity Assessment Tool (MDAAT). This tool has been developed by IMACS. This is a comprehensive tool that captures the physician’s assessment of disease activity of muscle, skin, joints, gastrointestinal tract, lung, and other organ systems. The MDAAT is a combined tool that includes the Myositis Disease Activity Assessment Visual Analog Scale (MYOTAC) and the Myositis Intention to Treat activities Index (MITAX).

The MYOACT is a series of physician’s assessments of disease activity in various organ systems using a VAS to assess severity of activity that has been modified from the Vasculitis Activity Index (42) The MYOACT consists of a 10-cm VAS for each organ system to score the overall severity of activity in each and a global extra-muscular VAS. For the MYOTAC, each organ system has a single VAS; a global extra-muscular activity VAS is also scored.

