APPENDIX D1.

IMACS definition of minimal clinical improvement, PRINTO definition of minimal, moderate, and major improvement and PRINTO criteria of inactive disease**

IMACS definition of minimal improvement	PRINTO definition of minimal improvement	PRINTO definition of moderate clinical improvement	PRINTO definition of major clinical improvement	PRINTO definition of inactive disease
≥ 20% of improvement in at least 3 of 6 core set measures, with ≤ 2 of the remaining worsening by > 25% (muscle strength cannot worsen)	≥ 20% of improvement in at least 3 of 6 core set measures, with ≤ 1 of the remaining worsening by ≥ 30% (muscle strength cannot worsen).	≥ 50% of improvement in at least 3 of 6 core set measures, with ≤ 1 of the remaining worsening by ≥ 30% (muscle strength cannot worsen).	≥ 70 of improvement in at least 3 of 6 core set measures, with ≤ 1 of the remaining worsening by ≥ 30% (muscle strength cannot worsen).	At least 3 of 4 criteria: CMAS ≥ 48; MD global Activity VAS ≤ 0.5 cm; CK ≤ 150; MMT ≥ 78.

*IMACS, International Myositis Assessment and Clinical Studies Group

**PRINTO, Pediatric Rheumatology International Trials

References:

**Rider LG, Giannini EH et al. International consensus on preliminary definitions of improvement in adult and juvenile myositis. International Myositis Assessment and Clinical Studies Group. Arthritis Rheum. 2004 Jul;50(7):2281-90. Review.

**Ruperto N, Pistorio A et al. The Paediatric Rheumatology International Trials Organisation provisional criteria for the evaluation of response to therapy in juvenile dermatomyositis. Arthritis Care Res (Hoboken). 2010 Nov;62(11):1533-41

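### Section 2.1 and Appendix D1 give different rules for inactive disease (all four criteria with physician global ≤ 0.2, versus three of four with ≤ 0.5 cm), neither gives a scale for MMT ≥ 78, and the primary DOI's worsening clause is worded two ways

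*Combined protocol and SAP*

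**What the plan says.** **Inactive disease.** Section 2.1 joins CK ≤ 150, CMAS ≥ 48 and two further conditions, "MMT ≥ 78 and Physician Global Activity VAS ≤ 0.2", and refers to Appendix D. The global cut-off has no unit. Appendix D1 reads "At least 3 of 4 criteria: CMAS ≥ 48; MD global Activity VAS ≤ 0.5 cm; CK ≤ 150; MMT ≥ 78". Sections 2.1 and 15.0 both commit to reporting how often this state is reached.

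**MMT scale.** Section 14.0 offers two versions: "MMT- 8 is a set of 8 designated muscles tested unilaterally (potential score 0-80) or bilaterally (potential score 0-150"). Its score table totals 0 to 150. Inclusion criterion 6b uses the larger scale: "Is the MMT-8 score no greater than 125/150". Neither inactive-disease rule attaches a scale to 78.

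**Primary DOI.** Section 2.1 requires three of six core set measures to improve by ≥ 20%, with at most two worsening by ≥ 25%, and adds "worsening measures cannot include the muscle strength". The Synopsis agrees: "worsening measure cannot include the muscle strength". Section 2.1 cites Appendix D1 for this definition, but the appendix allows "≤ 2 of the remaining worsening by > 25% (muscle strength cannot worsen").

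**Use during the trial.** At the follow-up visits in Section 7.1, "Prednisone taper may commence using a predetermined schedule (section 5) if the patient has achieved the Definition of Improvement (DOI") and the physician rates the patient at least minimally improved. Entry to the open-label extension also depends on the DOI (Sections 3.0 and 7.1).

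**The concern.** An outcome defined two ways has no single value, and the documents do not say which text prevails. For inactive disease, the number of criteria required, the physician-global cut-off and the unstated MMT scale can each change a patient's classification. Section 2.1 and Appendix D1 cite the same publication (reference 41), so these cannot be two separate intended outcomes.

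The DOI matters more. It is the primary efficacy endpoint, set against a target of 6 of 10. It is also one of the conditions for starting the prednisone taper and for entering the extension, so staff must apply one reading at visits, well before any analysis. In an open-label, single-arm trial, a choice of wording made after outcomes are known would be hard to defend.

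**Working it through.** The plan gives no figure of its own on this point, so there is nothing to reproduce. The check sets the texts side by side and applies them to example patients.

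**1. Inactive disease: count and cut-off**

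| | Section 2.1 | Appendix D1 |
|---|---|---|
| Criteria required | four, joined by a plain conjunction | at least 3 of 4 |
| Physician global | ≤ 0.2, no unit | ≤ 0.5 cm |
| CMAS, CK | ≥ 48, ≤ 150 | ≥ 48, ≤ 150 |
| MMT | ≥ 78, no scale | ≥ 78, no scale |

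- Four pass/fail criteria give 2^4 = 16 patterns. All four met: 1 pattern. At least three met: 4 + 1 = 5 patterns. This is before the 0.2 versus 0.5 difference is counted.
- CMAS 50, CK 100, MMT 79/80, global 0.4: not inactive under Section 2.1 (0.4 > 0.2); inactive under Appendix D1 (4 of 4 met).
- CMAS 50, CK 100, MMT 79/80, global 3.0: not inactive under Section 2.1; inactive under Appendix D1 (3 of 4 met). Criterion 6 needs a physician global of at least 2.5 cm plus two other abnormal measures. These could be patient global and extra-muscular activity, so such a patient could be eligible and already count as inactive at week 0.

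**2. MMT scale**

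- 78/80 = 97.5%; 78/150 = 52%; the entry threshold is 125/150 = 83.3%.
- On 0–150, any score from 78 to 125 is abnormal at entry yet passes the inactive-disease strength criterion.
- CK 100, CMAS 48, MMT 100/150, global 2.5 cm: three of four met, so inactive under Appendix D1 while still at the entry minimum for physician global.
- Pro-rata conversion (0.975 × 150 = 146.25) does not repair this, because the neck counts once on both scales while each limb group counts once on one and twice on the other:
  - Neck 7, everything else 10: 7 + 140 = 147/150, but 7 + 70 = 77/80.
  - A 4-point limb deficit on one side only: 146/150, but 76/80 or 80/80 depending on the side scored.
  - With equal limbs, 78/80 corresponds to 146 (10 + 2 × 68), 147 (9 + 2 × 69) or 148 (8 + 2 × 70).

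**3. Primary DOI**

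- *Strength clause.* Three measures improve by 30% and MMT falls from 120 to 119: 1/120 = 0.8%. If the Section 2.1 clause means that strength may not be among the measures worse by ≥ 25%, this patient is a responder. Under Appendix D1 read literally, the patient is a non-responder.
- *Threshold.* Three measures, including strength, improve by 30% and the other three worsen by exactly 25%. Section 2.1 counts three worsened measures, so non-responder; Appendix D1 counts none, so responder. Exactly 25% is attainable: a VAS going from 4.0 to 5.0 cm is (5.0 − 4.0)/4.0 = 25%.
- *Effect of one reclassified patient.* Exact (Clopper–Pearson) 95% intervals are 26.2% to 87.8% for 6/10 and 18.7% to 81.3% for 5/10. The intervals overlap heavily, but the stated target is met in one case and missed in the other.

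**The case against.** The strongest reply is that the DOI conflict may be only apparent. Section 2.1 cites Appendix D1, and in the appendix the strength remark follows directly after the worsening threshold, in the IMACS column and in each PRINTO improvement column. It may be shorthand for strength not being among the measures that worsen by that much. Section 2.1 can equally be read as allowing no decline at all. On either view the strength clauses agree, and only ≥ 25% versus > 25% remains. That is a fair reading, but the documents do not state it, and the threshold still differs.

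It can also be said that inactive disease is descriptive and absent from the Section 3.1 secondary list, that 6 of 10 is a postulate with no test attached, and that Section 5.0 allows a taper without the DOI when the investigator judges that circumstances require it. All of this is true and limits the stakes. It does not give the inactive-disease frequency a single value, and the DOI remains one condition for the taper.

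Section 2.1 might be leaving the count to the appendix. The conjunction does not say so, and the 0.2 versus 0.5 difference survives that reading. Finally, 78 fits only the 0–80 scale sensibly. This supports naming that scale, because an analyst using the eligibility scale would otherwise apply 78/150. The 1-versus-5 count describes combinations of criteria and is not a predicted frequency.

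**Conclusion.** The point holds and should be fixed. The inactive-disease rules are incompatible: the physician-global cut-off differs on any reading, and the required count differs on the plain reading. MMT ≥ 78 has no stated scale, and on the scale used for eligibility it would pass patients whose strength counts as abnormal at entry. The DOI threshold differs between Section 2.1 with the Synopsis and Appendix D1. Whether the strength clause differs as well depends on a reading that the documents leave open.

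The size of the DOI problem ranges from patients at exactly 25% worsening (milder reading) to any patient with a decline in MMT (literal reading). One reclassified patient is enough to move 6/10 to 5/10. How many would be affected cannot be estimated from the documents, and the documents alone cannot show which cut-offs match the cited publications.

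**What to change.** Before outcomes are analysed:

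1. Reconcile Section 2.1, the Synopsis and Appendix D1 to one DOI text checked against reference 38. State whether the limit is ≥ 25% or > 25%, and whether the strength clause means any decline or a decline at that limit.
2. Put one inactive-disease rule in both places, checked against reference 41: one physician-global cut-off with its unit, and one count of criteria.
3. State that MMT ≥ 78 applies to the 0–80 unilateral MMT-8 taken from the bilateral form, with the scored side fixed in advance and no pro-rata conversion to 150.
4. Report how many patients already meet the inactive-disease rule at week 0 beside the week-24 frequency.

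The cost is a text correction in Section 2.1, the Synopsis and Appendix D1. No new data are needed, because the unilateral score can be read from the bilateral form. The downsides are that fewer patients may count as inactive, and that a one-sided score ignores weakness on the other side.

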2.2 SECONDARY OBJECTIVES

Steroid-sparing benefit will be obtained. ***We hypothesize that we can reduce daily corticosteroid therapy by at least 20% in this population of treatment-refractory patients.***

To this end, a standardized corticosteroid tapering regimen will be utilized (Section 5). All subjects will remain on their initial prednisone dose until at least the first follow-up visit (week 6) and until they meet the definition of improvement and are rated as 'much improved' by both the physician and the patient or parent. The prednisone dose may then be reduced according to the standardized steroid tapering schedule in Section 5.

- a) To examine response to treatment in individual core set measures of disease activity as developed by IMACS, including Physician and Patient/Parent global activity, Muscle strength (by manual muscle testing, MMT-8), Physical function (by HAQ/CHAQ), Muscle enzymes, and Extra-muscular activity (by the Myositis Disease Activity Assessment Tool, MDAAT).
- b) To examine other core set activity measures as developed by PRINTO, including the Childhood Myositis Assessment Scale (CMAS), the Disease Activity Score (DAS) and Health Related Quality of Life Questionnaire (Childhood Health Questionnaire (CHQ-PF50) for children or SF-36 for adults.

- c) To examine improvement in patient reported outcomes, including health-related quality of life and fatigue measures, including the PROMIS fatigue questionnaire and PedsQL fatigue questionnaire. Both patient and parent questionnaires will be obtained, for patients < 18 years of age.
- d) (optional Assessment by Dermatology) To examine improvement in cutaneous activity, using the Cutaneous Dermatomyositis Area and Severity Index (CDASI) and the Dermatology Life Quality Index (DLQI), as well as periungual nailfold capillary density. To document changes in cutaneous findings by standardized photography.
- e) To examine improvement in muscle inflammation by examining a thigh/pelvis STIR MRI at baseline and 6 month follow-up.
- f) To examine that disease damage does not increase while under treatment with abatacept, by examining the Myositis Damage Index (MDI) at baseline and 6 month follow-up.
- g) To examine improvement of biomarkers that may relate to disease pathogenesis and the mechanism of action of abatacept in JDM, including:
 - i. Immunophenotyping for CD4, CXCR3, IFN γ (TH1), CD4, CCR4, CRTH2, IL4 (TH2), CD4, CCR6, IL17a (TH17), CD4, CD25, Foxp3 (T regulatory cells), B cell markers and macrophage markers along with B71, B72, CTLA4, CT28 on fresh lymphocytes
 - ii. Isolation of T cells, B cells, dendritic cells, monocyte and macrophages, and freeze the isolated cells for subsequent molecular and functional analysis, including gene expression profiling
 - iii. Cytokine 30-plex panel on serum samples
 - iv. Peripheral blood mononuclear cells for RNA gene expression using a gene bead chip panel.
- h) To evaluate immunogenicity and the pharmacokinetics of SC abatacept by the trough concentrations at steady state.

